3.3 General Considerations

The FAS will be used for all analyses unless otherwise stated.

Descriptive summaries of continuous data will be done by following statistics, unless otherwise stated, n, mean, SD, minimum, median, and maximum as appropriate. Q1 and Q3 may also be shown.

Descriptive summaries of categorical data will be done as the number and percentage of subjects in each category for each treatment group. When appropriate, for study population the number of missing observations will be presented, and these will be included in the denominator when calculating percentages unless otherwise stated. For treatment emergent and shift tables number of observations will be used as denominator. For AE tables the denominator will be the number of participants within the analysis set.

In general the reported CIs will be 90% two-sided intervals.

A general rule is to present descriptive summary statistics (mean, SD, median, Q1, Q3, Confidence intervals (CI) and standard error (SE)) to 1 more decimal place than the individual values. The minimum and maximum values should be reported to the same number of decimal places as the individual values. In general, the maximum number of decimal places reported shall be three for any summary statistics. Categorical data presented as percentages will be presented to one decimal place.

When coding using MedDRA the most recent version of the MedDRA that have been released for execution at AstraZeneca or designee will be used.

3.3.1 General Study Level Definitions

3.3.1.1 Baseline

For alanine aminotransferase (ALT), aspartate aminotransferase (AST), total bilirubin, direct bilirubin, alkaline phosphatase (ALP) and international normalized ratio (INR) baseline is defined as the mean of the values obtained during the screening period including unscheduled visits and the day of first dose.

For ECG and vital signs, baseline is defined as the last non-missing value prior to first administration of dose i.e. post-dose assessment on the day of first administration is not to be used.

The baseline value will for all other data be defined as the last non-missing value prior to or on the same date as administration of the first dose, unless values on the same date are known to be both pre- and post-dose assessments in which case the pre-dose assessment will be used as baseline.

For Loop diuretic baseline definition see section [3.3.1.5](#).

3.3.1.2 Analysis Periods

Planned treatment period

The planned treatment period starts on the date of first administration and ends on date of Visit 6.

Follow-up period

Starts the day after planned treatment period and ends on earliest of date of withdrawal of consent, death and last clinical assessment.

On-study analysis period

Starts on the date of first administration of study intervention and ends on the earliest of date of withdrawal of consent, death and last clinical assessment.

On-treatment period

Starts on the date of first administration and ends on the earliest of 28 days following the date of last dose of IMP or the end of the on-study analysis period.

3.3.1.3 Study Day

‘Study Day’ will be calculated relative to the date of first dose of study treatment i.e.:

if Assessment Date < Date of First Dose of Study Treatment, then

Study Day = Assessment Date – Date of First Dose of Study Treatment

else if Assessment Date \geq Date of First Dose of Study Treatment, then

Study Day = Assessment Date – Date of First Dose of Study Treatment + 1

This means that Study Day 1 is the day of first dose, Study Day -1 is the day prior to the date of first dose, there is no Study Day 0.

3.3.1.4 Imputation of Incomplete dates

Incomplete prior medication, concomitant medication and adverse event dates

Partially or completely missing medication or adverse event (AE) start dates will be imputed as follows (unless below puts the date before the date of first dose of treatment, if so date of first dose will be used):

- If medication started prior to study start, marked as taken prior to study start in the CM electronic case report form (eCRF), start date of medication may not be imputed. If not ticked in the CRF, the bullets below will be applied.
- If the year is missing the year should be imputed as the year that subject received the first dose of study treatment.
- If the year is available and the month and day is missing, then impute the month as January and the day as 01.
- If the year and month is available and the day is missing, impute the day as 01 (the first day of the month).
- If the AE/ medication start date is completely missing, the date of first dose of treatment will be used.

Partially or completely missing medication or AE stop dates will be imputed as follows (unless below puts the date after the date of end of study, if so date of end of study will be used):

- If the year is missing the year should be imputed as the year of end of study.
- If the year is available and the month and day is missing, then impute the month as December and the day as 31.
- If the year and month is available and the day is missing, impute the day as the last of the month (e.g. 28, 29, 30 or 31).

If the AE/ medication end date is completely missing, the date of end of study will be used.

If the medication is marked as “Ongoing” the stop date will not be imputed. If the AE is still ongoing, AE not reported as resolved then the date will not be imputed.

The following imputed dates will only be used for analysis purpose and will remain as reported (partially or completely missing) in subject listings.

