3.3.1.5 Loop diuretic equivalents

Table 2 Loop-diuretic equivalents

Drug	Global dose equivalent ^a	Japan dose equivalent
Furosemide	40	40
Bumetanide	1	N/A
Torsemide	20	8
Azosemide	N/A	60
Etacrynic/Ethacrynic acid	50	N/A

^a Will be used for all countries except Japan.

For analyses of loop-diuretic equivalents, the cumulative actual loop equivalents taken will be compared to the what the participant would have taken if continued to take equivalents as he/she did at baseline.

3.3.1.6 eGFR, MELD score and Child-Pugh score calculations

eGFR

The participant's eGFR will be calculated based on two different equations. eGFR1 is according to the 2021 CKD-EPI equation, based on serum creatinine concentration alone (Inker et al, 2021). eGFR2 will be calculated based on both serum creatinine and serum cystatin C concentrations (Inker et al, 2021).

$$\text{eGFR1} = 142 \times \min(S_{\text{cr}}/\kappa, 1)^{-0.241 \text{ (if female)} / -0.302 \text{ (if male)}} \times \max(S_{\text{cr}}/\kappa, 1)^{-1.200} \times 0.9938^{\text{Age}} \times 1.012 \text{ [if female]}$$

$$\text{eGFR2} = 135 \times \min(S_{\text{cr}}/\kappa, 1)^{-0.219 \text{ (if female)} / -0.144 \text{ (if male)}} \times \max(S_{\text{cr}}/\kappa, 1)^{-0.544} \times \min(S_{\text{cys}}/0.8, 1)^{-0.323} \times \max(S_{\text{cys}}/0.8, 1)^{-0.778} \times 0.996^{\text{Age}} \times 0.963 \text{ [if female]}$$

Where:

S_{cr} = serum creatinine (mg/dL)

S_{cys} = serum cystatin C (mg/L)

κ = 0.7 for females; and 0.9 for males

min = minimum of S_{cr}/κ or 1

max = maximum of S_{cr}/κ or 1

MELD score

The Model for end stage liver disease score, MELD score, is calculated for each visit according to:

$$\text{MELD} = 3.78 \times \ln[\text{serum bilirubin (mg/dL)}] + 11.2 \times \ln[\text{INR}] + 9.57 \times \ln[\text{serum creatinine (mg/dL)}] + 6.43$$
 If bilirubin, INR and/or creatinine values are less than 1.0, the value is set as 1.0.

Child-Pugh score

Child-Pugh score is calculated according to table [Table 3](#).

Table 3 Child-Pugh Score

Clinical and laboratory criteria	Points		
	1	2	3
Encephalopathy	None	Mild to moderate (West Haven grade 1 or 2)	Severe (West Haven grade 3 or 4)
Ascites	None	Mild to moderate (diuretic responsive)	Severe (diuretic refractory)
Bilirubin (mg/dL)	< 2	2 - 3	> 3
Albumin (g/dL)	> 3.5	2.8 – 3.5	< 2.8
Prothrombin time Seconds prolonged INR	< 4 < 1.7	4 - 6 1.7 – 2.3	> 6 > 2.3
Child-Turcotte-Pugh class obtained by adding score for each parameter (total points)			

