3.3.2 Visit Window

For the purpose of analysing visit based data, analysis visit windows will be used and are based on first dose date. All scheduled and unscheduled visits occurring the day after first dose or later (including Early Termination visit), will be mapped to an appropriate visit. Unless specified otherwise visit based analyses will follow as shown in [Table 4](#).

Table 4 General visit windowing

Analysis visit label	Analysis visit window start day (day included) ^a	Analysis visit window end day (day included) ^a	Target Day ^a
Week 1	Day 2	Day 11	Day 8
Week 2	Day 12	Day 18	Day 15
Week 3	Day 19	Day 31	Day 22
Week 6	Day 32	Day 50	Day 43
Week 8	Day 51	Day 78	Day 57

a Relative to the date of first dose of study treatment.

For general visit based-summaries, if there is more than one value per subject within a visit window, the closest assessment to the target date is assigned, or the earliest in the event the values are equidistant from the nominal visit date.

Composite endpoints (key objective 1,2,7 and 8) will follow [Table 5](#).

Table 5 Composite endpoints visit windowing

Analysis visit label	Analysis visit window start day (day included) ^a	Analysis visit window end day (day included) ^a
Week 1	Day 1 for component of fluid retention AEs Day 2 for other components	Day 11
Week 2	Day 12	Day 18
Week 3	Day 19	Day 25
Week 6	Day 26	Day 48
Week 8	Day 49	Each subjects EOS ^b

a Relative to the date of first dose of study treatment.

b Given that EOS occurs on or after study day 49.

Data that has been collected daily (loop-diuretic and home weight) will be summarized using visit windowing presented in [Table 6](#).

Table 6 Home weight and Loop-diuretic visit windowing

Analysis visit label	Analysis visit window start day (day included) ^a	Analysis visit window end day (day included) ^a
Week 1	Day 2	Day 8
Week 2	Day 9	Day 15

Analysis visit label	Analysis visit window start day (day included) ^a	Analysis visit window end day (day included) ^a
Week 3	Day 16	Day 22
Week 4	Day 23	Day 29
Week 5	Day 30	Day 36
Week 6	Day 37	Day 43
Week 8	Day 44	Each subjects EOS ^b

a Relative to the date of first dose of study treatment.

b Given that EOS occurs on or after study day 49.

In general, for summaries of extreme data at a subject level, all observations will be included regardless of whether it is included in the by-visit data presentation, e.g. when deriving a statistic such as the maximum.

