4.2.3.3 Handling of Dropouts and Missing Data

For missing partial dates for loop-diuretics see section 3.3.1.4. Other missing data is assumed to be MAR and no imputation will be done.

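### The partial-date rule for loop diuretics has no limit against an adjacent record, so a replaced dose can overlap its replacement and a reduction can be reported as an increase (key objectives 5 and 6)

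*SAP*

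**What the plan says.** SAP 3.3.1.4 covers incomplete medication and AE dates together. For a stop date with month and year known, it says to "impute the day as the last of the month", "unless below puts the date after the date of end of study, if so date of end of study will be used". For a start date: "If the year and month is available and the day is missing, impute the day as 01 (the first day of the month"), "unless below puts the date before the date of first dose of treatment, if so date of first dose will be used". The only outer limits are therefore end of study and first dose. Records marked ongoing are exempt from stop-date imputation, but a replaced record is not ongoing.

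SAP 4.2.3.3, for key objectives 5 and 6, brings loop diuretics under this rule: "For missing partial dates for loop-diuretics see section" 3.3.1.4. SAP 3.3.1.5 then compares the cumulative equivalents actually taken with what "the participant would have taken if continued to take equivalents as he/she did at baseline". Neither section says what to do when two records of one treatment overlap. The only sensitivity analysis for this endpoint (SAP 4.2.3.5) replaces MMRM with ANCOVA and would use the same derived values.

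On how the data are held, the documents point two ways. Protocol 6.9 records each medication with start and end dates, dose and frequency. SAP 3.3.2, introducing Table 6 ("Home weight and Loop-diuretic visit windowing"), describes loop-diuretic data as gathered every day.

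**The concern.** Moving incomplete dates outward to the edges of the month is a sensible inclusive choice when the question is whether an AE or a medication falls in a period. A cumulative dose is a different quantity, because every added day adds a full daily dose. When one loop-diuretic dose replaces another, the old record can be stretched forward over the new one, or the new one back over the old one, and the participant appears to have taken both.

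The error always runs towards higher intake relative to the dose before the change. A participant whose dose was lowered can then contribute an increase to a key endpoint. With about 22 participants per arm, a few such values would be visible in the arm means.

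**Working it through.** The documents give no figure for this endpoint or for date imputation, so there is nothing to reproduce. The check is day-by-day arithmetic.

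**Inputs.** The date rules are those of SAP 3.3.1.4. One equivalent is 40 mg furosemide (SAP Table 2). Planned Week 6 is Day 43 (Protocol Table 1). The Week 6 window is Days 37-43 (SAP Table 6).

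**Assumptions.** There is one record per dose, records are summed, and baseline is the dose before the change. The doses and dates are illustrative.

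**Formula.** Let the old dose be *a* and the new dose *b* equivalents/day, with the change on Day *c*. Let *s* be the days the old record is stretched forward, and *r* the days the new record is stretched back. Over Days 1-43:

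- True change = -(a - b)(43 - c + 1)
- Change under the rule = a·s + b·r - (a - b)(43 - c + 1)

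**Illustration.** First dose is 25 March, so Day 43 is 6 May. The dose goes from 80 to 40 mg/day on 16 April, which is Day 23, so a = 2, b = 1 and 43 - 23 + 1 = 21 days. Stretching the stop to 30 April gives s = 15. Stretching the start to 1 April gives r = 15.

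| Missing | Calculation | Result |
|---|---|---|
| None (true) | -1×21 | -21 |
| Stop day | 2×15 - 21 | +9 |
| Start day | 1×15 - 21 | -6 |
| Both | 2×15 + 1×15 - 21 | +24 |

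**Week 6 window alone, same case.** Days 37-43 are 30 April to 6 May. With the stop day missing, alone or with the start day, 30 April counts at 3 against 2 (+1) and the other six days at 1 against 2 (-6), giving -5. With only the start day missing it is -7. The true value is -7, so the sign stays right here.

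**Other dates can flip the Week 6 window.** With first dose on 18 March and the same change date, Days 37-43 are 23-29 April. With both days missing, each day counts at 3 against 2, giving +7 against a true -7.

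**Switch at equal equivalents.** Take furosemide 40 mg to torsemide 20 mg/day (equal in the global column of Table 2), with dates as in the illustration. The true change is 0. The rule gives +15 with one day missing and +30 with both.

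**Grid.** First dose falls on each of 365 consecutive dates from 1 June 2024, the change on each of Days 2-43 (365 × 42 = 15,330 cases), and end of study on Day 57. For 80 to 40 mg/day with the pre-change dose as baseline, the reported change has the wrong sign as follows:

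| Missing | Days 1-43 | Days 37-43 |
|---|---|---|
| Stop day only | 9,534 (62%) | 6,360 (41%) |
| Start day only | 4,641 (30%) | 987 (6%) |
| Both | 12,306 (80%) | 6,432 (42%) |

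These are shares of possible dates, given that the day or days are missing. If Day 1 use is the baseline instead, the both-missing share over Days 1-43 is 9,453 (62%) and the start-day share 27%. The other four entries do not change.

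**The case against.** The strongest objection is to the premise. If loop-diuretic use really is captured daily, as SAP 3.3.2 says, a replaced dose has no stop date to impute and no overlap arises. That sentence cannot be set aside, and the CRF is not supplied. Against it, 4.2.3.3 expressly provides for partial loop-diuretic dates, which would be needless with daily capture. The Schedule of Activities lists concomitant medication at visits and schedules daily home measurement only for body weight. The two SAP statements conflict, so the premise is plausible but not established.

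Second, no passage says that overlapping records are added. SAP 3.3.1.5 speaks of equivalents actually taken, and two doses of a replaced drug on one day are not that. Programming specifications or data cleaning might resolve the overlap. This stands as a limit: summing is the natural reading of a cumulative comparison, but it is an inference.

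Third, the trigger may be rare. Medication is reviewed at each visit, entries undergo source data verification, and the day must be missing while the month is known. This also stands, since no frequency is given.

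A reader might take the 80% as the risk in this trial. The documents do not support that: it requires both days missing and a halved dose, with possible dates weighted equally. A reader might also infer bias for or against the combination arm. The rule is the same in every arm, and nothing in the documents shows how dose changes or partial dates will be distributed between arms.

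**Conclusion.** The gap in the rule is real: SAP 3.3.1.4, as applied by 4.2.3.3, sets no limit against an adjacent loop-diuretic record. The consequence is conditional on dose changes being held as start/stop records and on those records being summed. Under both conditions, a missing stop day on the replaced record or a missing start day on the replacing one overstates intake whenever the imputed date moves, and it can turn a reduction into an increase. In the illustration the error over Days 1-43 is 15 equivalents (start day missing), 30 (stop day missing) or 45 (both missing) on a true change of -21.

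A sign reversal is not automatic. It depends on the dates, on the size of the reduction and on whether Week 6 use is accumulated from first dose or taken within Days 37-43. A missing start day alone seldom reverses the Week 6 window.

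The effect on the group comparison cannot be sized, and the study performs no formal hypothesis test. The severity is minor to moderate. The lack of a stated loop-diuretic baseline and accumulation window in 3.3.1.5 is a separate point. It affects the figures here but is not the cause of the overlap.

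**What to change.** Add an exception to SAP 3.3.1.4 for loop diuretics only. It applies when one record replaces another (a new dose, or a switch between loop diuretics), not to add-on use:

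- An imputed stop may not fall on or after the start of the replacing record.
- An imputed start may not fall on or before the stop of the replaced record.
- If one of the two dates is known, use it as the change date.
- If both days are unknown, use one single change date within the known month. Narrow it by visit dates only where visit records show which visits the change fell between.

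Reconcile the description of daily collection in 3.3.2 with the partial-date provision in 4.2.3.3. If use is in fact captured daily, say so and remove the partial-date reference. Keep the present rule for AEs.

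The cost is a few SAP sentences, a flag separating replacing from add-on records, and a programming check for overlaps. With both days unknown the answer stays approximate. In the illustration, if visit records place the change between Visit 5 (15 April) and Visit 6 (6 May), the April part of that interval is 16-30 April and its midpoint is 23 April. The result is then -1×14 = -14 against a true -21: the right sign, and 7 equivalents out instead of 45. Without that visit information the interval is the whole month.

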3.3.1.5 Loop diuretic equivalents

Table 2 Loop-diuretic equivalents

Drug	Global dose equivalent ^a	Japan dose equivalent
Furosemide	40	40
Bumetanide	1	N/A
Torsemide	20	8
Azosemide	N/A	60
Etacrynic/Ethacrynic acid	50	N/A

^a Will be used for all countries except Japan.

For analyses of loop-diuretic equivalents, the cumulative actual loop equivalents taken will be compared to the what the participant would have taken if continued to take equivalents as he/she did at baseline.

3.3.1.6 eGFR, MELD score and Child-Pugh score calculations

eGFR

The participant's eGFR will be calculated based on two different equations. eGFR1 is according to the 2021 CKD-EPI equation, based on serum creatinine concentration alone (Inker et al, 2021). eGFR2 will be calculated based on both serum creatinine and serum cystatin C concentrations (Inker et al, 2021).

$$\text{eGFR1} = 142 \times \min(S_{\text{cr}}/\kappa, 1)^{-0.241 \text{ (if female)} / -0.302 \text{ (if male)}} \times \max(S_{\text{cr}}/\kappa, 1)^{-1.200} \times 0.9938^{\text{Age}} \times 1.012 \text{ [if female]}$$

$$\text{eGFR2} = 135 \times \min(S_{\text{cr}}/\kappa, 1)^{-0.219 \text{ (if female)} / -0.144 \text{ (if male)}} \times \max(S_{\text{cr}}/\kappa, 1)^{-0.544} \times \min(S_{\text{cys}}/0.8, 1)^{-0.323} \times \max(S_{\text{cys}}/0.8, 1)^{-0.778} \times 0.996^{\text{Age}} \times 0.963 \text{ [if female]}$$

Where:

S_{cr} = serum creatinine (mg/dL)

S_{cys} = serum cystatin C (mg/L)

κ = 0.7 for females; and 0.9 for males

min = minimum of S_{cr}/κ or 1

max = maximum of S_{cr}/κ or 1

MELD score

The Model for end stage liver disease score, MELD score, is calculated for each visit according to:

$$\text{MELD} = 3.78 \times \ln[\text{serum bilirubin (mg/dL)}] + 11.2 \times \ln[\text{INR}] + 9.57 \times \ln[\text{serum creatinine (mg/dL)}] + 6.43$$
 If bilirubin, INR and/or creatinine values are less than 1.0, the value is set as 1.0.

Child-Pugh score

Child-Pugh score is calculated according to table [Table 3](#).

Table 3 Child-Pugh Score

Clinical and laboratory criteria	Points		
	1	2	3
Encephalopathy	None	Mild to moderate (West Haven grade 1 or 2)	Severe (West Haven grade 3 or 4)
Ascites	None	Mild to moderate (diuretic responsive)	Severe (diuretic refractory)
Bilirubin (mg/dL)	< 2	2 - 3	> 3
Albumin (g/dL)	> 3.5	2.8 – 3.5	< 2.8
Prothrombin time Seconds prolonged INR	< 4 < 1.7	4 - 6 1.7 – 2.3	> 6 > 2.3
Child-Turcotte-Pugh class obtained by adding score for each parameter (total points)			
Class A = 5 to 6 points (least severe liver disease)			
Class B = 7 to 9 points (moderately severe liver disease)			
Class C = 10 to 15 points (most severe liver disease)			

Abbreviations: INR = International Normalised Ratio.

3.3.1.7 Subgroups

Below defines the different subgroups to be analysed as stated in this document:

- **CCI** [REDACTED] patients

3.3.2 Visit Window

For the purpose of analysing visit based data, analysis visit windows will be used and are based on first dose date. All scheduled and unscheduled visits occurring the day after first dose or later (including Early Termination visit), will be mapped to an appropriate visit. Unless specified otherwise visit based analyses will follow as shown in [Table 4](#).

Table 4 General visit windowing

Analysis visit label	Analysis visit window start day (day included) ^a	Analysis visit window end day (day included) ^a	Target Day ^a
Week 1	Day 2	Day 11	Day 8
Week 2	Day 12	Day 18	Day 15
Week 3	Day 19	Day 31	Day 22
Week 6	Day 32	Day 50	Day 43
Week 8	Day 51	Day 78	Day 57

a Relative to the date of first dose of study treatment.

For general visit based-summaries, if there is more than one value per subject within a visit window, the closest assessment to the target date is assigned, or the earliest in the event the values are equidistant from the nominal visit date.

Composite endpoints (key objective 1,2,7 and 8) will follow [Table 5](#).

Table 5 Composite endpoints visit windowing

Analysis visit label	Analysis visit window start day (day included) ^a	Analysis visit window end day (day included) ^a
Week 1	Day 1 for component of fluid retention AEs Day 2 for other components	Day 11
Week 2	Day 12	Day 18
Week 3	Day 19	Day 25
Week 6	Day 26	Day 48
Week 8	Day 49	Each subjects EOS ^b

a Relative to the date of first dose of study treatment.

b Given that EOS occurs on or after study day 49.

Data that has been collected daily (loop-diuretic and home weight) will be summarized using visit windowing presented in [Table 6](#).

Table 6 Home weight and Loop-diuretic visit windowing

Analysis visit label	Analysis visit window start day (day included) ^a	Analysis visit window end day (day included) ^a
Week 1	Day 2	Day 8
Week 2	Day 9	Day 15

Analysis visit label	Analysis visit window start day (day included) ^a	Analysis visit window end day (day included) ^a
Week 3	Day 16	Day 22
Week 4	Day 23	Day 29
Week 5	Day 30	Day 36
Week 6	Day 37	Day 43
Week 8	Day 44	Each subjects EOS ^b

a Relative to the date of first dose of study treatment.

b Given that EOS occurs on or after study day 49.

In general, for summaries of extreme data at a subject level, all observations will be included regardless of whether it is included in the by-visit data presentation, e.g. when deriving a statistic such as the maximum.

